14.4. Exploratory Analyses

Overall survival (OS) is defined as the interval of time between the date of the first dose of study drug and the date of death due to any cause. For subjects surviving at the time of OS analysis, the time of death will be censored at the date of last contact. The reason for death may be included in the summary.

14.5. Safety Analyses

All safety analyses, unless otherwise specified, will be performed on the Safety Population. The incidence of AEs and SAEs will be summarized. Laboratory test results, vital signs, and their changes from baseline, will be summarized using descriptive statistics. Abnormal values will be flagged.

14.6. Determination of Sample Size and Criteria for Early Stopping Due to Futility

The primary objective of this study is to evaluate the ORR obtained in subjects with R/R FL and WT EZH2 status, treated with the combination of rituximab and tazemetostat. Given the historical data with single agent rituximab (McLaughlin, 1998; Leonard, 2019), the Sponsor would consider the combined regimen to be of no further interest if the ORR were 50% or less, but of considerable interest if the ORR were at least 70%.

Simon's two-stage design (Simon, 1989) will be used. The null hypothesis that the true response rate is 50% will be tested against the one-sided alternative. In the first stage, 15 subjects will be accrued. If there are 8 or fewer responses in these 15 subjects, the regimen will be considered as futile.

Subject enrollment will continue during futility analysis. If 9 responses or greater (CR + PR) are seen in the initial 15 subjects, additional subjects will be accrued for a total of 54 evaluable subjects. The Sponsor expects 80% of enrolled subjects to have WT EZH2 status. Consequently, the study will enroll approximately 43 WT subjects as well as approximately 11 MT subjects. With an estimated early dropout rate of 10%, this study estimates a total accrual of 59 subjects.

For the primary analysis, the null hypothesis will be rejected if 27 or more responses (CR + PR) are observed in the first 43 evaluable subjects regardless of mutation status. This design yields a one-sided type I error rate of 0.05 and power of 0.801 when the true response rate is 70%.

If the primary analysis is successful, full analysis will be conducted once 54 evaluable subjects are available regardless of mutation status. Subjects in the FAS will be stratified to 2 subgroups depending on their EZH2 mutation status (WT vs MT).

With an estimated 54 eligible subjects in the combined FAS, rates of individual AEs can be estimated to within at most \pm 14% (95% confidence interval). Any AE with a true rate of at least 5% is likely to be observed at least once (93% chance).

Assuming accrual takes place over 24 months, with at least an additional 12 months of follow-up for progression, there would be approximately 65% power to rule out a benchmark median PFS of 12 months against the alternative of a true PFS of 18 months (one-sided, 0.05 level test) in the primary analysis subset of 43 subjects with at least 26 PFS events. If PFS is similar in both subsets regardless of EZH2 status, then there would be 80% power for the same analysis in the combined FAS of 54 subjects with at least 33 PFS events.

The reporting of response rate in the MT EZH2 subset (anticipated to be 11 subjects) will have very little precision and is exploratory only. Note, the subjects with MT EZH2 status will be included in all primary safety analyses.

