6. TRIAL OBJECTIVES AND ENDPOINTS

6.1. Objectives

6.1.1. Primary Objective

• To assess the objective response rate (ORR; complete response + partial response [CR + PR]) of tazemetostat in combination with rituximab in subjects with R/R FL and with WT EZH2 status.

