6.2. Endpoints

6.2.1. Primary Endpoint

• ORR, defined as the proportion of all subjects with WT EZH2 status achieving a CR or PR according to the 2014 Lugano Classification (Appendix 3) as assessed by Investigator and blinded independent review committee (IRC) at the following time points: Cycle 3, Cycle 6, Cycle 12, Cycle 18, and Cycle 24

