7.2. Number of Subjects

Approximately 59 subjects (assuming a 10% early drop-out rate) will be enrolled to obtain approximately 54 evaluable subjects in the final statistical analysis:

- Approximately 43 evaluable subjects with WT EZH2 (primary study population) and
- Approximately 11 evaluable subjects with MT EZH2

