14.2. Primary Efficacy Analyses

ORR is defined as the proportion of subjects achieving a CR or PR according to the 2014 Lugano Classification (Appendix 3) as assessed by Investigator and blinded IRC at the following time points: Cycle 3, Cycle 6, Cycle 12, Cycle 18, and Cycle 24.

Subjects with a best response of unknown/non-evaluable response will be treated as non-responders, (i.e., they will be included in the denominator only when calculating the percentage). ORR will be presented with corresponding 2-sided 95% confidence intervals (CIs). This analysis will be performed on a subset of the FAS that includes all subjects with WT EZH2 status.

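### The primary question is about wild-type EZH2 subjects, but the Simon futility and success rules count all comers, so 0.05 and 0.801 apply to wild-type only if mutant subjects have the same response rate

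*Protocol*

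**What the plan says.** **WT as the primary population.** Protocol 6.1.1 sets the primary objective as the response rate of "tazemetostat in combination with rituximab in subjects with R/R FL and with WT EZH2 status". Section 6.2.1 defines the endpoint as "ORR, defined as the proportion of all subjects with WT EZH2 status achieving a CR or PR". Section 14.2 says of the primary estimate and its 95% confidence interval: "This analysis will be performed on a subset of the FAS that includes all subjects with WT EZH2 status". Section 7.2 plans "Approximately 43 evaluable subjects with WT EZH2 (primary study population) and" about 11 with MT. Section 14.6, SAP 3.2.1 and SAP 4.1 also state the objective for WT. The Synopsis sample size text and SAP 4.2 leave out the WT limit.

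**All comers as the decision population.** Sections 7.1, 14 (Futility Analysis Set) and 14.1 base the futility look (8 or fewer responses) on the first 15 subjects of any mutation status. Section 14 defines the Primary Analysis Set in the same way for the first 43. Section 14.6, repeated in SAP 3.2.1, has the null "rejected if 27 or more responses (CR + PR) are observed in the first 43 evaluable subjects regardless of mutation status" and quotes error 0.05 and power 0.801. The result gates the next step: "If the primary analysis is successful, full analysis will be conducted once 54 evaluable subjects are available regardless of mutation status".

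**Pooling assumption.** For PFS, Section 14.6 contrasts a "primary analysis subset of 43 subjects with at least 26 PFS events" with the combined set of 54, and gives the condition for pooling: "If PFS is similar in both subsets regardless of EZH2 status, then there would be 80% power". No visible text gives one for response. SAP Appendix 1, which holds the sample size calculation, is redacted.

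**A second test.** SAP 4.3 names a one-sample chi-square test of the 50% null at one-sided 0.025, with no population.

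**The concern.** The number 43 is used in two ways: as the planned WT count (80% of 54) and as the first 43 subjects of any status. At 80% WT, the first 43 hold about 34 WT subjects and the first 15 about 12. The quoted error and power therefore belong to a test of the pooled rate, while the stated question is the WT rate.

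If the MT rate exceeds 50%, MT responses can carry the rule over 27 while the WT rate sits at the null. If the MT rate is below 70%, a WT rate of 70% is detected less often than stated. The Section 14.2 WT analysis has no threshold that could settle the matter, and SAP 4.3 brings in a different significance level. A reader cannot tell which population and which level decide success.

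**Working it through.** **Inputs.** Null 50%, alternative 70%, stop at 8 or fewer of 15, reject at 27 or more of 43, 80% WT, 54 evaluable (Section 14.6). The MT response rate is not given, so it is an assumption and is varied.

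**1. Reproduce the plan.** For one common rate p,

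P(reject) = Σ over x = 9 to 15 of P[Bin(15, p) = x] × P[Bin(28, p) ≥ 27 − x].

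- p = 0.50: 0.0499 (stated 0.05)
- p = 0.70: 0.8044 (stated 0.801, a small difference)

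The plan's figures are those of a single common rate.

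**2. Mixed population.** With 80% WT, the rate per subject is 0.8 × WT + 0.2 × MT. For example, WT 50% and MT 70% give 0.40 + 0.14 = 0.54. Putting the pooled rate into the same formula:

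| Assumed MT rate | Pooled rate, WT 50% | WT error | Pooled rate, WT 70% | Power |
|---|---|---|---|---|
| 40% | 0.48 | 2.9% | 0.64 | 54% |
| 50% | 0.50 | 5.0% | 0.66 | 64% |
| 60% | 0.52 | 8.2% | 0.68 | 73% |
| 70% | 0.54 | 12.7% | 0.70 | 80% |
| 80% | 0.56 | 18.7% | 0.72 | 87% |
| 90% | 0.58 | 26.2% | 0.74 | 91% |

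Error is at most 0.05 when the MT rate is 50% or less. Power is at least 0.80 when the MT rate is 70% or more. Between the two, neither figure holds.

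**3. Sensitivity.** A fixed split (12 WT + 3 MT, then 22 + 6) changes little: error 0.129 at WT 50% and MT 70%, power 0.639 at WT 70% and MT 50%. With a WT share of 75% to 85%, error at MT 70% is 0.155 to 0.103, and power at MT 50% is 0.594 to 0.687.

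**4. The SAP 4.3 test.** Without continuity correction, z = (x − 21.5)/√(43 × 0.25) = (x − 21.5)/3.279.

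- x = 27: z = 1.677, one-sided p = 0.047, which fails 0.025
- x = 28: z = 1.982, one-sided p = 0.024, which passes

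The two rules disagree at exactly 27 of 43.

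**5. The rule applied to WT only.** Step 1 applies directly with p as the WT rate, so error is 0.0499 and power 0.804 whatever the MT rate. Reaching 43 WT takes 43/0.8 = 53.75 evaluable subjects on average. The chance of at least 43 WT is 50% at 53 evaluable (59 × 0.9 = 53.1) and 61% at 54. If fewer are reached, the smallest boundary with error at most 0.05 and the same first stage is:

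| WT reached | Reject at | Error | Power |
|---|---|---|---|
| 37 | 24 | 0.042 | 0.754 |
| 38 | 25 | 0.032 | 0.728 |
| 39 | 25 | 0.045 | 0.774 |
| 40 | 26 | 0.034 | 0.752 |
| 41 | 26 | 0.048 | 0.791 |
| 42 | 27 | 0.037 | 0.771 |
| 43 | 27 | 0.0499 | 0.804 |

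Averaged over the WT number reached (capped at 43, with a boundary for every number), error is 0.045 and power 0.785 at 53 evaluable, and 0.046 and 0.789 at 54.

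**The case against.** **The null may be a common one.** The 50% benchmark comes from single-agent rituximab data that the documents do not split by EZH2 status. If tazemetostat adds nothing in either group and the baseline rates match, the error is 5%. Reaching 12.7% needs no gain in WT and 20 points in MT. This stands: the table shows what could happen and does not predict it.

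**A reader might infer that the WT error is in fact inflated**, because Sections 5.2.1 and 5.3 report greater sensitivity in MT models. The documents do not support that step. Those data are preclinical and single-agent, the combination experiments in 5.3 are not split by EZH2 status, and no clinical MT rate is given. The direction is unknown.

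**A reader might also infer that the plan has no success criterion for WT at all.** That goes too far. SAP 4.3 names no population, but SAP 4.1 makes the primary objective WT, and both documents let the SAP prevail over the protocol's statistics. SAP 4.3 could be read as the WT criterion. It then conflicts with the 0.05 rule in SAP 3.2.1.

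**An all-comer futility look is defensible.** Section 7.1 ties futility stopping to subject safety, and MT subjects are exposed too. That supports the look, but it does not make 0.05 and 0.801 WT figures.

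**The redacted appendix may state a pooling assumption.** This is possible, so the claim is limited to the visible text.

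**Conclusion.** The mismatch stands. The stated error and power are correct for a pooled response rate. They hold for WT only if MT subjects respond at 50% when WT do, and at 70% when WT do. For an assumed MT rate of 50% to 70% and 80% WT, the WT error is 5.0% to 12.7% and power is 64% to 80%. At or below 50% the error is within 0.05, and at or above 70% the power is at least as stated. These sizes rest on the assumed MT rate and WT share, on the 15 being part of the 43, and on one response definition at both looks.

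It should not be inferred that any reported result is affected. SAP 5.2, 8 and 9 say that the study ended with 5 treated subjects and that no futility or efficacy analysis will be done. The point is worth correcting in the record, and it matters if the design is reused.

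**What to change.** **Minimum.** State in Section 14.6, the Synopsis and SAP 3.2.1 that 0.05 and 0.801 refer to the pooled population and hold for WT only under equal response rates. Reconcile SAP 4.3 with the one-sided 0.05 rule. This costs only wording.

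**Preferred, for any reuse.** Apply both stages to WT subjects: futility on the first 15 WT, success at 27 or more of the first 43 WT.

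- Make the 15 part of the 43 and use one response definition at both stages. Section 14 now requires a Cycle 6 assessment for the Futility Analysis Set but any one post-baseline assessment for the Primary Analysis Set. Without this, 0.0499 and 0.804 are not assured.
- Specify the exact boundary for every WT number that may be reached, chosen from the WT count alone. The list must go below 38, because the chance of 37 or fewer WT is 5.1% at 53 evaluable.
- Align the Synopsis, Sections 7.1, 14, 14.1 and 14.6, and SAP 3.2.1, 4.2 and 4.3 on one population and one significance level. Keep pooled response as the secondary endpoint it already is.

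**Cost of the preferred change.** The futility look moves from 15 to about 19 evaluable subjects on average (15/0.8 = 18.75). It takes 23 to have at least a 95% chance of 15 WT (97% at 23, 94% at 22). Enrollment continues meanwhile. The primary analysis moves from 43 to about 54 evaluable and so merges with the full analysis, which makes the gate between them redundant. Average power is about 0.785 to 0.79, because 43 WT will often not be reached.

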7. INVESTIGATIONAL PLAN

7.1. Overall Study Design and Plan

[figure not shown]
This is a phase 2, multicenter, open-label study of oral tazemetostat in combination with rituximab in subjects with R/R FL. Subjects will enroll into a single, open-label arm of the study where they will each be stratified based on EZH2 mutation status (MT or WT). Additionally, subjects will be stratified by previous experience with rituximab (rituximab refractory or rituximab-naïve). Stratification will occur during data analysis rather than at enrollment. This study is designed to evaluate the safety and efficacy of tazemetostat in combination with rituximab in subjects previously treated with at least 2 prior systemic lines of therapy for FL and features early futility stopping to maintain subject safety.

The first stage will enroll 15 subjects regardless of EZH2 mutational status. Futility analysis will be performed when the Cycle 6 Day 1 tumor assessment data are available for the first 15 subjects. If there are 8 or fewer responses in these 15 subjects, the study will be considered futile. Enrollment will continue during the interim futility analysis. If 9 responses or greater are seen in the initial 15 subjects, additional subjects will be accrued for a total of 54 evaluable subjects regardless of mutation status.

Based on Simon's 2-stage design, the primary analysis will occur after 43 evaluable subjects regardless of mutation status are available. Enrollment will continue during the primary analysis. Full set analysis will occur once data from 54 evaluable subjects regardless of mutation status are available.

This study includes a 28-day screening period, a 2-year (24-cycle) treatment period, and a follow-up period. During the treatment period, subjects will receive tazemetostat in combination with rituximab in 28-day cycles for the first 6 cycles followed by tazemetostat alone in 28-day cycles for the remaining 18 cycles, or until disease progression, unacceptable toxicity, or withdrawal of consent. Disease assessments will be performed at screening, Cycle 3 Day 1, Cycle 6 Day 1, Cycle 12 Day 1, Cycle 18 Day 1, and Cycle 24 Day 1.

Figure 1: Study Schema

Note: Enrollment will not stop during futility analysis or primary analysis.

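### The plan contradicts itself on whether the 54-subject analysis, which carries the wild-type response rate named as primary, is run when the pooled 43-subject test fails

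*Protocol*

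**What the plan says.** Two versions of the same step stand in the documents.

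- **Conditional.** Protocol 14.6: "If the primary analysis is successful, full analysis will be conducted once 54 evaluable subjects are available regardless of mutation status". The synopsis (Sample Size Justification) and SAP 3.2.1 carry the same condition.
- **Unconditional.** Protocol 7.1: "Full set analysis will occur once data from 54 evaluable subjects regardless of mutation status are available". The synopsis (Study Design) agrees, so the synopsis also disagrees with itself.

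Success is defined on WT and mutant (MT) subjects together: "the null hypothesis will be rejected if 27 or more responses (CR + PR) are observed in the first 43 evaluable subjects". Accrual to 54 depends only on the first-stage result. With 9 or more responses in 15, "additional subjects will be accrued for a total of 54 evaluable subjects", and Section 7.1 keeps enrollment open during the primary analysis.

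The primary endpoint (Protocol 6.2.1) is the response rate in WT subjects. Protocol 14.2 says of it: "This analysis will be performed on a subset of the FAS that includes all subjects with WT EZH2 status". Section 14.3 puts PFS, DOR and the pooled, MT and rituximab-refractory response rates on the Full Analysis Set (FAS) as well. Section 14 defines the FAS as dosed subjects with a baseline and a post-baseline tumor assessment. Neither reaching 54 nor passing a test is part of that definition.

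**The concern.** The 43-subject test pools WT and MT subjects, so it does not itself deliver the WT response rate. That rate is specified only on the FAS, and in 14.6 the WT/MT split of the FAS comes straight after the conditional sentence. Taken literally, a failed pooled test cancels the full-set analysis, and with it the result for the stated primary endpoint, although accrual to 54 has been authorised and much of the data would exist.

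Two things are at stake. First, no section says what is reported for WT subjects after a failed test, so the choice could be made with results in hand. Second, if full-set estimates appear only after a success, they come from a selected set of trials and are too high on average.

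**Working it through.** **Inputs (Protocol 14.6).** Null 50%, target 70%. First stage 15 subjects: "If there are 8 or fewer responses in these 15 subjects, the regimen will be considered as futile". Success is 27 or more of 43. Full set 54, so the three blocks are 15, 28 and 11 subjects, with responses X1, X2 and X3. One common response rate p is assumed for WT and MT.

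**Step 1: reproduce the design.** The plan states: "This design yields a one-sided type I error rate of 0.05 and power of 0.801 when the true response rate is 70" (percent). The exact calculation is

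P(success) = Σ, for x = 9 to 15, of P(X1 = x) · P(X2 ≥ 27 − x), with X1 ~ Bin(15, p) and X2 ~ Bin(28, p).

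This gives 0.0499 at p = 0.50 and 0.8044 at p = 0.70. The stated 0.05 and 0.801 are reproduced closely enough for this purpose.

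**Step 2: how often the condition alone withholds the analysis.** These are trials that pass futility and then fail at 43:

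P(X1 ≥ 9) − P(success).

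| True rate | Passes futility | Success at 43 | Passes, then fails |
|---|---|---|---|
| 50% | 0.304 | 0.050 | 0.254 |
| 55% | 0.452 | 0.155 | 0.297 |
| 60% | 0.610 | 0.349 | 0.261 |
| 70% | 0.869 | 0.804 | 0.064 |

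**Step 3: mean 54-subject response rate under each rule.**

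- Futility rule only (7.1 wording): (E[X1 | X1 ≥ 9] + 39p) / 54.
- Reported only after success (14.6 read literally): (E[X1 + X2 | success] + 11p) / 54.

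At p = 0.60 the first is (10.220 + 23.4)/54 = 0.623 and the second is (28.984 + 6.6)/54 = 0.659.

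| True rate | Futility only | Success required | Added by the condition |
|---|---|---|---|
| 50% | 54.2% | 62.1% | 7.9 points |
| 55% | 58.2% | 63.8% | 5.7 points |
| 60% | 62.3% | 65.9% | 3.6 points |
| 70% | 70.8% | 71.6% | 0.8 points |

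(Differences are taken before rounding.)

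**Step 4: the WT rate itself.** Simulating 400,000 trials with 80% WT subjects and a common rate puts the mean WT rate after success within 0.1 point of the pooled figures above. If MT subjects respond better (assumed values), the WT bias is smaller. WT 50% with MT 70% gives 59.6% after success against 53.4% after futility alone. WT 60% with MT 75% gives 64.5% against 61.8%.

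**The case against.** The strongest reply is that 14.6 is a sample-size section and does not define the analyses. Sections 14.2 and 14.3 do, and they say the WT, PFS, DOR and subgroup analyses are performed, with no success condition. The FAS does not depend on success either. On this view the conditional sentence governs only whether a separate look at 54 takes place. Section 19 also promises a public summary of results whatever the outcome. This stands to the following extent. A reader might infer that the WT rate is reported only after a favourable pooled result, but the documents do not establish that: it is the literal consequence of 14.6 and one of two available readings. The reply does not remove the conflict. Section 19 does not say which analyses the summary contains, and Section 14 lets the SAP govern inconsistencies while SAP 3.2.1 carries the conditional version.

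A reader might also blame the condition for every trial without success at a true 70%, about 20% (1 − 0.804 = 0.196). That is too strong. Of those 19.6 points, 13.1 are futility stops, which Section 7.1 shares; only 6.4 come from the condition. Likewise, the full excess after success (12.1, 8.8, 5.9 and 1.6 points at 50%, 55%, 60% and 70%) is not all due to it, because futility selection alone gives 4.2, 3.2, 2.3 and 0.8.

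Finally, the SAP (Sections 5.2, 8 and 9) records termination with 5 treated subjects and no futility or efficacy analysis. That removes any effect on this trial's results, but does not make the design text consistent.

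**Conclusion.** The contradiction is real, and it touches the primary endpoint. Three places make the 54-subject analysis conditional on the pooled 43-subject test, two do not, and 14.2 requires the WT response rate without a condition. Under the literal reading of 14.6, the full-set analysis is lost because of the condition alone in about 25%, 30%, 26% and 6% of trials at true rates of 50%, 55%, 60% and 70%. If results are reported only after success, the condition adds about 7.9, 5.7, 3.6 and 0.8 points to the mean reported rate beyond futility selection. The effect is largest where the regimen is of least interest and under one point at the design target. The exact figures assume one common response rate; the WT-only figures also assume 80% WT subjects. The upward bias depends on the literal reading being followed, which the documents leave unsettled.

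**What to change.** Reconcile the five places. Delete the opening conditional clause of the full-analysis sentence in Protocol 14.6, in the synopsis sample-size text and in SAP 3.2.1, so that they agree with Protocol 7.1 and the synopsis design text. Add one sentence stating that the FAS analyses (WT, MT, pooled and rituximab-refractory response rates, PFS and DOR) are reported on all enrolled subjects who qualify for the FAS, whatever the 43-subject result.

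This does not remove the bias from the futility gate (4.2, 2.3 and 0.8 points at 50%, 60% and 70%). The text should say so, and could add an estimate and confidence interval that account for the two-stage design.

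The cost is wording, plus analysis of data already collected if the 43-subject test fails. The test, alpha, power and planned enrollment do not change. Because the trial ended with 5 subjects, the correction serves the record and any reuse of the design.
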